### **G. Indicate the study design/phase by checking the appropriate box(s).**

Phase I

Phase I/II

Phase II

Phase II/III

Phase III  
Phase IV  
Other:  
Case-Control  
Cohort  
Cross-sectional  
◆ Randomized, parallel group  
Randomized, cross-over  
◆ Placebo-Controlled  
Single Blind  
◆ Double Blind  
Triple Blind

## **DRUGS, BIOLOGIC DRUGS AND DEVICES**

### **13. Drugs and Biologic Drugs**

**A. Does this study involve an investigational drug or biologic drug?**

No

**B. Does this research involve an FDA-approved and marketed drug or biologic drug?**

Yes

### **14. Devices**

**A. Does this research involve an investigational device?**

No

**B. Does this research involve an FDA-approved and marketed device?**

No

## **CONFIDENTIALITY AND PRIVACY**

### **15. Confidentiality and Privacy**

**A. Will research data be stored:**

**1) On a secure server at UNMC/TNMC/CH&MC/UNO?**

Yes

**2) On a local hard drive?**

Yes

**a) Describe the location of the hard drive.**

The office of the PI in the department of psychiatry at UNMC.

**b) Describe how the local device will be secured (e.g. in a locked room).**

It will be stored in a locked cabinet, in a locked room (PI's office).

**c) Is the hard drive encrypted?**

Yes

**3) On a portable computer?**

No

**4) On a flash drive?**

No

**5) In a database accessible through the internet?**

No

**6) In hard copy?**

Yes

**a) Will the hard copies be stored at UNMC/TNMC/CH&MC/UNO during the conduct of the study (i.e. not the long term storage location)?**

Yes

**b) Will the hard copies be stored off campus during the conduct of the study (i.e. not the long term storage location)?**

No

**c) Describe the physical methods to protect the hard copies (e.g. locked file cabinet or locked briefcase).**

The hard copies will be locked in a cabinet in the PI's locked office in the outpatient clinic of the department of psychiatry, UNMC.

**d) Will hard copies ever be transported from one site to another site (on or off campus)?**

No

**7) Other?**

Yes

**a) Describe where data will be stored.**

The MRI data will be stored at the Boys Town National Research Hospital.  
The MEG data will be stored at the MEG center of UNMC.

**b) Describe how data will be secured.**

Both Boys Town National Research Hospital and MEG center of UNMC will have secured server where the fMRI and MEG data are stored. This is a standard procedure of neuroimaging facilities.

The primary investigator will have access to those servers of the Boys Town National Research Hospital and the MEG center of UNMC remotely via internet, to download the neuroimaging data (fMRI and MEG) to the computer at the department of psychiatry secured in a safe place. This access will be granted by the passwords provided to the primary investigator from those facilities. The primary investigator will conduct neuroimaging data analysis. The computer for storing neuroimaging data and analysis will be accessed only by using password, and the door of the room where the computer is located is to be locked.

**B. Will any of the following subject identifiers be recorded (at any time) in association with the research data?**

Yes

**1) Indicate the subject identifiers that will be recorded:**

- ◆ Name
- ◆ Postal address information: street address, city, county, precinct, ZIP code
- ◆ All elements of dates (except year) related to an individual (e.g. birth, admission, discharge)
- ◆ Telephone numbers
- Fax numbers
- ◆ Electronic mail addresses
- ◆ Social Security numbers
- ◆ Medical Record numbers
- Health plan beneficiary numbers
- Account numbers
- Certificate/license numbers
- Vehicle identifiers and serial numbers, including license plate numbers
- Device identifiers and serial numbers
- Web Universal Resource Locators (URLs)

Internet Protocol (IP) address numbers  
Biometric identifiers, including finger and voice prints  
Full face photographic images [and any comparable images]  
No identifiers will be maintained

**2) Will a unique subject identifying number, characteristic or code be used to protect the confidentiality of the data? This includes codes assigned by the investigator to link data to other identifiers like the subject's name or medical record number.**

Yes

**a) Where will the key, that links the unique subject identification code to the subject's name or other identifier, be stored?**

The subject identifying number will be created by consecutive number series designated to each subject.

The key that links the unique subject identification code will be maintained by the study coordinator in a cabinet secured in the locked office (separate from the office where the data are stored) of the outpatient clinic of the department of psychiatry, UNMC. This is accessible to the PI and the coordinator.

**3) What is the justification for recording the specific identifiers listed above?**

- ◆ Schedule appointments  
Collect continuous clinical information from the medical records
- ◆ Follow-up with subjects  
Link stored tissue with subject identification for it to be withdrawn in the future if requested
- ◆ Other. Explain. ssn needed for payment of study stipend

**4) How long will the subject identifiers be maintained in association with the research data?**

Subject identifiers will be maintained until research aims are achieved and completed.

**5) How will the research data be archived or destroyed when the data is no longer required?**

All hard copies will be confidentially shredded.

The fMRI, MEG and anatomical data will be stored in a secured server (COINS) that was developed specifically for the neuroimaging data for two weeks before being transferred to the UNMC computer at the department of psychiatry for further analysis of BOLD responses. The server is automatically set up that the data will be destroyed permanently by

cryptographic erase after this two weeks of period.

Once the study is completed, the data stored in the computer will be destroyed by the standard sanitization process by UNMC IT team. This will involve the cryptographic erase. This will be executed in accordance with UNMC policy No. 6016, destruction/disposal of private and confidential information

**6) Will research data that contain subject identifiers be disclosed to any other investigators at UNMC, TNMC, UNO or CH&MC who are not listed in Section I of this application?**

No

**7) Will research data that contain subject identifiers be disclosed to any investigators outside of UNMC, TNMC, UNO or CH&MC?**

No

**8) Will research data that contain subject identifiers be disclosed to any commercial sponsor, contract research organization (CRO) or Data and Safety Monitoring Board (DSMB)?**

No

**9) Will research data that contain subject identifiers be disclosed to any other external organization or entity (e.g., NCI cooperative groups)?**

No

**10) Will research data be shared with third party payers?**

No

**C. What provisions will be in place to protect the subject's privacy? Check all that apply.**

- ◆ Obtaining consent in a private conference room or area
  - ◆ Ensuring that only personnel listed on the IRB application Section I.3(A-E) are present during the consent process
  - ◆ Ensuring that the fewest number of individuals possible are aware of the subject's participation in the research.
  - ◆ Ensuring that the research activities are performed in as private of a place as possible
- Other. Explain.

**D. Does this research involve data banking at UNMC, TNMC, UNO or CH&MC for future**

research that is not related to this study?

No

**E. Does this research involve data banking by an outside organization (e.g. NCI Cooperative Group, pharmaceutical company) for future, unspecified research that are not integral to the current research?**

No

## RISK/BENEFIT ASSESSMENT

### 16. Potential Risks

**What are the potential risks associated with each research procedure, intervention, evaluation and/or test? If data are available, estimate the probability that a given harm may occur and its potential reversibility.**

Risks and discomfort can be expected from the interviews and examinations, the fMRI, the MEG, the pregnancy testing and drug screening, the administration of nasal spray oxytocin and placebo. Risks and discomforts with each study procedure will now be described.

## Interview and examinations

Psychiatric interview and mental status examination can evoke emotional discomfort and anxiety when it is regarding personal information or past/present psychiatric history taking. The participants and their parents will be instructed to inform the investigators of this immediately so the interview and examination can be re-directed or ceased should this happen. Also participants and their parents will be instructed that they don't have an obligation to answer all the questions, and they can withdraw from the protocol any time. The interviews and examinations will be done by either a board certified child and adolescent psychiatrist, or an advanced practice registered nurse. All investigators who will conduct the interviews and examinations are trained mental health providers with extensive research experience in child and adolescent psychiatry.

## Functional MRI

Functional MRI scans are widely regarded as a safe, noninvasive procedure for visualization of brain tissue in both adults and children. This study will be performed on an FDA approved scanner at Boys Town National Research Hospital. FDA standards for minimal risk MRI require that four criteria be met: 1) a static magnetic field no greater than 4T, 2) specific absorption rates a) no greater than 4W/kg for the entire body for 15 minutes, b) no greater than 3W/kg over the head for 10 minutes, and c) no greater than 8W/kg in any gram of tissue in the head or torso or 12W/kg in any gram of tissue in the extremities for five

minutes, 3) a time rate of change in the field that does not produce physical discomfort or painful nerve stimulation, and 4) a peak sound pressure level that does not exceed 140 dB or A-weighted R.M.S. pressure level that does not exceed 99dBA with hearing protection. Each of the guidelines will be monitored throughout the study to ensure that none are exceeded.

Participants are at risk for injury from an MRI study if they have metal objects in their bodies such as pacemakers, aneurysm clips (metal clips on the wall of a large artery), metallic prostheses, cochlear implants, or shrapnel fragments. Parents will be asked about the presence of such objects using the standard pre-MRI safety checklist from the department of radiology of the Boys Town National Research Hospital. In addition, at MRI visits 1 and 2, parents will fill out a form to identify any new medical events since the child was screened/last scanned. Individuals with these contraindications will not receive an MRI study scan. During a scan, a loud rhythmic tapping or banging sound is heard. This noise is caused by the switching of the gradient coils that is necessary to produce the image. The noise from the scanner is loud enough to damage hearing, especially in people who already have hearing loss. Protective earplugs are inserted by trained staff, and a head support is used to minimize movement. If the hearing protection comes loose during the scan, the investigators will fix it right away. There are no known long-term risks of MRI scans. Participants will be closely observed at all times by staff who will terminate the scan if a child appears distressed by the experience.

Through the MRI scans a neurological disorder can be discovered. Should this occur, the child will be referred for clinical assessment to an appropriate health care provider.

One of the risks of an anatomical MRI which will be conducted with functional MRI is discovery of incidental findings. This may include benign anatomical variation (e.g. Chiari I malformation) or more serious findings (e.g. brain tumor). The radiology clinicians at the Boys Town National Research Hospital will review the anatomical MRI no later than 7 days after the image is obtained. If there is an incidental finding, this will be reported to [name] who will then report it to the parent/guardian of the child. [name] will discuss referral for additional evaluation or treatment with the parent/guardian as appropriate, including referral to the primary care provider or if requested, to an appropriate department of University of Nebraska Medical Center for appropriate further assessment and treatment.

## MEG

In regard to MEG, subjects may experience discomfort from the paste and tape that is used to attach electrodes and head coils to the skin surface. Such discomfort may include skin irritation or accidental hair removal.

Participants will be closely observed at all times by staff who will terminate MEG scan if a child appears distressed by the experience.

## **Pregnancy testing and urine drug screening**

The risk associated with performing a pregnancy test is finding out that one of our participants is indeed pregnant. It will be notified to the participants and the parents accordingly.

### **Administration of nasal spray oxytocin and placebo**

The risk associated with oxytocin nasal spray administration are common side effects of oxytocin, including light headedness/vertigo, drowsiness/sleepiness, dry throat/mouth, nasal irritation, runny nose, abdominal discomfort, anxiety, elevation of mood, and headache. Also there are risks related to nasal spray, including irritation of nasal membrane, nosebleed, post-nasal drip, and irritation by bad taste/smell (MacDonald et al., 2011).

Although those side effects of oxytocin are possible to occur with administration of oxytocin nasal spray, it is not any more common than placebo in 45 randomized double-blind placebo trials including population of children and adolescents (MacDonald et al., 2011; Oya, Matsuda, Matsunaga, Kishi, & Iwata, 2015). Also short period time frame (2 weeks) of the trial will significantly lower the risk of side effects. We expect the potential risk of nasal spray itself such as irritation of nasal membrane, post-nasal drip, and irritation by bad taste/smell to be minor and transient, even when it occurs.

Participants will be examined as part of screening for their physical health and previous history of and response to oxytocin administration, and also will be monitored by either child and adolescent psychiatrist or nurse practitioner during the treatment time frame of oxytocin nasal spray or placebo. Should any side effect occur, we will monitor the course of side effects while the participant is in the time frame of treatment, providing visit to the outpatient clinic of the department of psychiatry at University of Nebraska Medical Center for check-up of sign/symptom and physical/neurological examination. If any significant side effect occurs, the participant will be referred for further clinical care as necessary.

### **Buccal Cheek Brush for genetic sampling**

The Potential risk of buccal cheek brush for genetic sampling includes irritation of buccal cheek, minor bleeding of mucosa, and uncomfortable sense/taste of the brush. We expect the potential risk of buccal cheek brush to be minor and transient. If any of these events happen during the procedure, we will provide close monitoring while the participant is in the outpatient clinic of the department of psychiatry at University of Nebraska Medical Center. If any significant adverse event happens, the participant will be referred for further clinical care as necessary.

### **Genetic testing of oxytocin receptor**

The potential risk of genetic testing of the oxytocin receptor is minimal. This will not contain any information regarding personal identification of the participants. Thus, the result of genetic testing will not be given to the participants or their parent/guardian. It will not be stored or banked for future study either.

#### **17. Risk Classification**

##### **What is the overall risk classification of the research?**

Minimal risk

◆ Greater than minimal risk

Significant risk

#### **18. Minimization of Risk**

##### **A. Will the research utilize procedures already being performed on the subjects for diagnostic or treatment purposes?**

No

##### **B. Describe how the subjects of the research will be monitored by the investigators and other research personnel to ensure their safety.**

Participants will be closely monitored at all times by UNMC and Boys Town National Research Hospital research staff who will terminate the scanning of MRI and/or MEG if a participant appears distressed by the experience. The participants will be observed via monitor screens while they are performing neuropsychological tasks in the scanner of MRI and MEG. Vital signs including blood pressure and pulse rate may be obtained if any participant showed distress.

Participants will be monitored for any side effect from oxytocin or placebo nasal spray during their visit to the outpatient clinic of the department of psychiatry at University of Nebraska Medical Center, during their treatment period (14 to 21 days). Participants and their parents will be given of the contact number to the outpatient clinic for any clinical concern or occurring of side effect. The research team will provide extra clinical visit if it is clinically necessary during the course of treatment.

##### **C. Describe the process by which the PI will be informed and how the PI, in turn, will inform other research staff about events concerning subject safety (including (a) interim results; (b) adverse events; (c) unanticipated problems involving risks to subjects or others; (d) noncompliance; (e) complaints).**

1) At UNMC/TNMC/CH&MC and/or UNO (check all that apply).

Not applicable. The PI is the only person listed in Section I of the IRB Application.

- ◆ By email or campus mail (for events which do not constitute immediate subject safety hazards)

- ◆ By phone

- ◆ By in-person meeting

- ◆ By scheduled submission of case report forms

Other. Explain.

**2) At external study sites under the oversight of the Joint Pediatric IRB as applicable (check all that apply).**

By email or mail (for events which do not constitute immediate subject safety hazards)

By phone

By in-person meeting or teleconference

By scheduled submission of case report forms

- ◆ Other. Explain. n/a

**D. Describe the auditing plan for research conducted:**

**1) Within the Organization (UNMC, TNMC, UNO or CH&MC), identify who will conduct the audits and specify the audit frequency.**

The audit will be conducted by the PI, the secondary investigators, and participating personnel at the end of every month throughout the duration of the study.

**2) At external study sites under the oversight of the Joint Pediatric IRB, identify who will conduct the audits and specify the audit frequency.**

N/A.

**E. Is there is an independent DSMB for this study?**

Yes

**Will you be submitting the DSMB charter?**

Yes

**F. Describe the specific criteria by which the investigator would withdraw individual subjects from the research (for example, medical criteria, such as specific toxicity or lack of efficacy or non-medical criteria, such as non-compliance).**

**Withdrawal Criteria**

1. Initiation of any medication that may have psychotropic effects (newly introduced antidepressants, antipsychotics, anxiolytics, stimulants, and non-stimulant ADHD medications).

2. Discovery of neurologic disorder (including seizures) or anatomical abnormality of brain (including brain neoplasm, hydrocephalus) during participation.
3. Discovery of substance abuse or dependence.
4. Inability of the participant to complete fMRI or MEG due to claustrophobia despite previous questioning.
5. Participants who do not want to continue with the study.
6. Participants who cannot or will not cooperate with study procedures.
7. Participants who experience strong discomfort or develop side effect following the administration of oxytocin or placebo nasal spray.
8. Participants who experience significant worsening of psychiatric symptoms that warrant change of treatment (such as inpatient psychiatric hospitalization).

**G. Describe the specific criteria for halting or early termination of the study (for example statistical evidence of unacceptable toxicity or early demonstration of efficacy or lack of efficacy).**

The study would be halted in followings;

1. Early evidence showing lack of efficacy on irritability or worsening of irritability by oxytocin treatment: After the preliminary phase of the study (10 patients on each arms of oxytocin and placebo trial), if it turns out that children and adolescents experience significant worsening of their psychiatric/behavioral symptoms, or have no change in their psychiatric/behavioral symptoms, we then will consider terminating the study.
2. MEG and/or fMRI become inoperable
3. Serious injury related to procedure (MEG, fMRI, or oxytocin administration) occurs

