## **CHARACTERISTICS OF THE SUBJECT POPULATION**

### **4. Accrual**

**Is this study conducted solely at sites under the oversight of the Joint Pediatric IRB (e.g. UNMC, TNMC, CH&MC, UNO)?**

Yes

**A. What is the total number of subjects (per group, as applicable) needed to complete the research in order to achieve the scientific objectives of the research?**

104 subjects are needed to complete the trial (52 per treatment group).

**B. What is the statistical or other justification for the total number of subjects needed to complete the research in order to achieve the scientific objectives of the research?**

The primary outcome is the change of Affective Reactivity Index (ARI) from the baseline to the last visit. A sample size of n=52 per group will provide 80% power to detect a difference between the group means of -4.0 in the change of ARI of -4.0 at the significance level of

0.05 using a two-sided two-sample t-test, assuming the mean of -4.0 and the standard deviation of 7.2 in the oxytocin group, and the mean of 0 and the standard deviation of 7.2 in the placebo group.

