#### **C. Based on the anticipated number of screen failures and/or subject withdrawals, what is the maximum number of subjects that will need to be consented in order to achieve the scientific objectives of the research?**

A maximum of 140 subjects will be consented

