The second fMRI and MEG scans will be completed after 14-21 days of oxytocin/placebo treatment. The final research assessment will be completed at that time. The duration of oxytocin treatment (14 to 21 days) will be decided by the scheduling and completion of MRI visit 2 and MEG visit 2.

Compliance with medication and adverse effects will be assessed at each visit. If during the course of the study it is discovered that the participant has a disorder or condition that would disqualify him/her (e.g., unexpected side effect of oxytocin that will necessitate cessation of the treatment or medical compromise that will make it impossible to continue oxytocin treatment), but needs further evaluation, the participant will be immediately referred for further clinical assessment and intervention to their primary care provider or, if requested, an appropriate department at the University of Nebraska Medical Center.

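### The withdrawal list removes a child from the research for any side effect, two other sections handle the same event differently, and no final ARI is provided for after withdrawal

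*Combined protocol and SAP*

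**What the plan says.** Three parts of the combined protocol and SAP deal with a child who has a side effect.

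- **Item 18.F, Withdrawal Criteria.** The form asks when the investigator would withdraw a subject from the research. Criterion 7 answers: "Participants who experience strong discomfort or develop side effect following the administration of oxytocin or placebo nasal spray". The adjective attaches to discomfort; a side effect carries no threshold. Criterion 8, on psychiatric worsening, does carry one.
- **Item 16, Administration of nasal spray oxytocin and placebo.** If any side effect occurs, "we will monitor the course of side effects while the participant is in the time frame of treatment", with clinic check-ups. A significant one leads to referral. Withdrawal is not mentioned. The section lists runny nose, dry mouth, drowsiness and headache among the common effects. It also says that side effects have been no more common than on placebo and that the short trial lowers the risk.
- **Item 12.B, Oxytocin/placebo administration.** The example of a disqualifying event is an "unexpected side effect of oxytocin that will necessitate cessation of the treatment".

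On numbers, item 4.A says "104 subjects are needed to complete the trial (52 per treatment group"), and item 4.C says "A maximum of 140 subjects will be consented", an allowance meant for screen failures and withdrawals together. The primary outcome is the ARI change from baseline to the last visit, and the closing ARI is taken at the final research assessment. No section describes obtaining it from a withdrawn child. The internal pilot (item 12.F) will assess retention, but no expected rate is stated.

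**The concern.** The same mild event can be handled in different ways depending on which section staff consult. Under criterion 7 as worded, a child on either spray who reports a runny nose or a headache leaves the research. Under item 16 the natural reading is that the child stays in and is watched.

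The literal rule turns a common event into a missing primary outcome, because leaving the research also means missing the final assessment. That uses up the allowance between consented and completing children, and power falls if the allowance runs out. It also makes retention depend on how individual staff read the text. The pilot's retention estimate would then reflect that variation without resolving it.

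**Working it through.** **Inputs from item 4.** "A sample size of n=52 per group will provide 80% power to detect a difference between the group means of -4.0", at "0.05 using a two-sided two-sample t-test", "assuming the mean of -4.0 and the standard deviation of 7.2 in the oxytocin group" and mean 0 with the same SD on placebo. Completers needed: 104. Maximum consented: 140.

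**Inputs assumed.** The documents give no side-effect rate and no screen-failure rate. The calculation varies side-effect withdrawal from 10 to 40% and loss before randomisation from 0 to 20%. A withdrawn child is counted as a non-completer, since no final ARI is provided for.

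**Step 1: reproduce the plan's figure.** Standardised difference = 4.0/7.2 = 0.556. For a two-sample t-test with n per arm, the noncentrality is 0.556 × √(n/2) on 2n − 2 degrees of freedom. Solving for 80% power gives n = 51.84, so 52 per arm, with power 80.1% at 52. The plan's figure reproduces.

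**Step 2: the allowance.** 140 − 104 = 36 places, and 36/140 = 25.7% for all losses together.

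**Step 3: withdrawal rate at which the expected number of completers falls to 104.** With R randomised, the limit is (R − 104)/R.

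| Lost before randomisation (assumed) | R | Limit on withdrawals |
|---|---|---|
| 0% | 140 | 36/140 = 25.7% |
| 5% | 133 | 29/133 = 21.8% |
| 10% | 126 | 22/126 = 17.5% |
| 15% | 119 | 15/119 = 12.6% |
| 20% | 112 | 8/112 = 7.1% |

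**Step 4: power and the chance of 104 completers.** Expected completers = R(1 − w), where w is the withdrawal rate. Power uses half of that number per arm in the formula of step 1. The chance is the binomial probability of at least 104 completers out of R.

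| w | R = 140: completers, power, chance | R = 119: completers, power, chance |
|---|---|---|
| 10% | 126.0, 87.2%, above 99% | 107.1, 81.3%, 86% |
| 20% | 112.0, 83.0%, 96% | 95.2, 76.5%, 2% |
| 30% | 98.0, 77.7%, 16% | 83.3, 70.7%, below 0.1% |
| 40% | 84.0, 71.1%, below 0.1% | 71.4, 63.9%, below 0.1% |

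At 5 to 10% withdrawal with no more than 10% other loss, the chance of reaching 104 is at least 99%. The outcome therefore turns on two rates that the documents do not give.

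**The case against.** The best defence is that the three sections can be read as tiers: any effect is monitored, a significant one is referred, and one that forces cessation disqualifies. On that view criterion 7 is a loosely worded tolerability criterion, and item 12.B is a referral rule with an example. Item 16 never says outright that dosing continues; the treatment time frame could simply mean the 14 to 21 days. This stands in part. Continued participation is the natural reading of item 16 but is not stated. The tiers, however, have to be supplied by the reader, because criterion 7 has no severity word and its consequence is leaving the research.

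A reader might infer a larger power loss by applying withdrawals to 104 randomised children: 46, 41, 36 or 31 per arm, and power of 75, 70, 64 or 58%, at 10, 20, 30 or 40%. The documents do not support that. Item 4 asks for 104 children who complete and allows 140 consents to cover losses, so the figures in step 4 are the relevant ones.

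A reader might also infer that the rule biases the comparison between arms. Criterion 7 applies to both sprays in a double-blind trial, and item 16 reports side effects as no more common than on placebo. Unequal loss remains possible, but nothing in the documents shows it.

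The pilot's retention check could reveal heavy loss early. That is a partial safeguard, and it leaves the conflicting instructions in place.

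**Conclusion.** The inconsistency is real whatever the side-effect rate: criterion 7 has no threshold, while items 16 and 12.B both imply that some side effects do not end participation. Its practical weight comes from the missing provision for a final ARI after withdrawal, which makes each such withdrawal a lost primary outcome.

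The size is conditional. If withdrawals are around 10% and few children are lost at screening, 104 completers are still reached. If 15% are lost before randomisation, the target is missed on average above 12.6% withdrawal, and power is about 76.5% at 20%. Whether the trial would in fact miss its target cannot be determined from the documents. The main expected harm is fewer completers in both arms. This merits correction, but it does not show that the design fails.

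**What to change.** Reconcile items 12.B, 16 and 18.F so that one statement governs when a side effect ends treatment, and have the other two sections refer to it. Which clinical rule applies is for the sponsor to decide.

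Separately, state that stopping the spray does not by itself end data collection. The final ARI should be sought from, and analysed for, every randomised child whose consent has not been withdrawn, in the arm to which the child was assigned.

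The cost is protocol wording and a few extra final questionnaires from children who stopped the spray. Those children then count towards the effect of assignment, which may be smaller than the effect in children who took the full course.
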